### 1. Abstract

- a. Provide no more than a one page research abstract briefly stating the problem, the research hypothesis, and the importance of the research.

Over the past several decades, age-adjusted, population-based rates of tracheostomy has doubled (Mehta, Syeda, Bajpayee, Cooke, Walkey & Wiener, 2015). Acutely ill patients with tracheostomy have reported that the ability to speak is fundamental to social communication and to their personal identities, and conversely, the lack of voice often leads to frustration and feelings of confinement (Carroll, 2007; Foster, 2010). The use of one-way speaking valves (OWSV) is supported in the literature as a way to restore speech in patients with tracheostomy who are on or off of mechanical ventilation (Hess, 2005). The benefits of speech restoration and the consequences of its delay suggest that the early use of OWSV in patients with tracheostomy may be beneficial. However, the literature lacks clear evidence for the optimal timing to initiate the use of OWSV or its clinical outcomes.

The timing for initiating OWSV use varies internationally, and the timing most appropriate for specific patient populations is unknown. In the United States, evaluation for speech using an OWSV has traditionally been at least 48 hours following tracheostomy procedure. On the other hand, speech language pathologists (SLPs) in Europe and Australia indicated (personal communication) that they initiate OWSV evaluation as early as 4 hours after the tracheostomy procedure. Furthermore, the safety of early use of OWSV may be related to the type of tracheostomy procedure itself. A representative from Passy-Muir, the manufacturer of OWSV, stated in an interview that the 48 hour waiting period in the United States is based on traditional open surgical tracheostomy, rather than the percutaneous procedure. Notably, percutaneous tracheotomy has been shown to be associated with a lower overall postoperative complication rate when compared with open operative tracheotomy, and the use of percutaneous technique is on the rise (Freeman, Isabella, Lin, & Buchman, 2000).

Therefore, we propose a prospective randomized clinical trial - pilot study to investigate the safety of early use of OWSV in patients undergoing a percutaneous tracheostomy.

### 2. Objectives (include all primary and secondary objectives)

#### **Specific Aim 1: Identify patients who would benefit from early use of the OWSV.**

Hypothesis 1a: Several factors such as age, sex, educational level, primary diagnosis, indication for tracheostomy, co-morbidities, and severity of illness will significantly contribute to early tolerance of the OWSV.

#### **Specific Aim 2: Determine the effect of the early use of the OWSV on the quality of speech.**

Hypothesis 2a: The increase in the speech intelligibility scores from pre- to post- assessment will be significantly higher in the patients who receive early OWSV compared to those who receive it the traditional way 48 hours after undergoing a tracheostomy.

Research Question 2b: Is the duration of speech longer for patients who start using OWSV earlier compared to those who start late?

#### **Specific Aim 3: Determine the effect of early use of the OWSV on clinical outcomes.**

Hypothesis 3a: The increase in the health-related quality of life scores from pre- to post- assessment will be significantly higher in the patients who receive early OWSV compared to those who receive it the traditional way 48 hours after undergoing a tracheostomy.

Hypothesis 3b: There will be no significant changes in the rate of complications between patients receiving early versus standard use of the OWSV.

Hypothesis 3c: Patients who begin to use the OWSV early will have a significantly shorter lengths of stay in the ICU than patients who start using OWSV after 48 hours.

**3. Background** (briefly describe pre-clinical and clinical data, current experience with procedures, drug or device, and any other relevant information to justify the research)

Current standard of care to wait 48 hours following tracheostomy procedure to initiate OWSV assessment and treatment, however, there is scant evidence in the literature justifying this amount of time. 201 patients out 272 patients who received a tracheostomy received SLP consult for in 2014. Based on prior data from the tracheostomy database 30% of mechanically ventilated and / or tracheotomized patients tend to be awake and interactive, and attempt to communicate.

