**Sequence and timing:**

- A. Screening by Tracheostomy Nurse Practitioner following percutaneous tracheotomy
1. Glasgow Coma Scale (GCS)
  2. Richmond Agitation Sedation Scale (RASS)
- B. Speech-Language Pathologist consult is placed for patients meeting study inclusion criteria
- C. Patient consent is obtained by Tracheostomy Nurse Practitioner or Speech-Language Pathologist
- D. Randomization into Intervention and Control groups
- E. Session 1 within 12-24 hours following percutaneous tracheotomy:
1. Both groups complete pre-assessment consisting of the following:
    - i. Electronic Patient Records (POE, EPR, or EPIC)
      1. Demographic Data
      2. Patient Characteristics
      3. Sequential Organ Failure Assessment (SOFA)
    - ii. Confusion Assessment Method for the ICU (CAM-ICU)
    - iii. Health-related quality of life survey, Quality of Life – Mechanical Ventilation (QOL-MV)
    - iv. Tracheostomy-related assessment
      1. Trach size
      2. Mechanical ventilation status
      3. Secretions & tolerance of cuff deflation
      4. Presence of complications
        - i. Bleeding at stoma
        - ii. Subcutaneous air
        - iii. Infection at stomal site
        - iv. Pneumothorax
        - v. Accidental decannulation
  2. Intervention Group completes standard SLP evaluation and OWSV trial:
    - i. SLP evaluation includes the following to assess candidacy for OWSV trial:
      1. Level of alertness
      2. Cranial nerve exam
      3. Ability to cough
      4. Ability to tolerate cuff deflation
      5. Ability to tolerate finger occlusion
      6. Vocal quality
    - ii. If appropriate, OWSV will be trialed and assessed for the following:
      1. Duration of tolerance
      2. Change in vital signs
      3. Vocal quality
      4. Presence of air trapping
      5. Sentence Intelligibility Test
    - iii. Recommendations are made for OWSV use outside of SLP supervision
      1. Supervision requirement (RN, Respiratory therapist, trained family, independent)
      2. Duration of OWSV use
  3. Control Group receives no further evaluation or treatment during Session 1, which constitutes current standard of care.
- F. Session 2 within 48-60 hours following percutaneous tracheotomy:
1. Both groups complete post-assessment:

Date: 2/06/18

Principal Investigator: [name]

Application Number: IRB00080981

[figure not shown]
- i. Electronic Patient Records (POE, EPR, or EPIC)
    1. Demographic Data
    2. Patient Characteristics

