    3. Sequential Organ Failure Assessment (SOFA)
  - ii. Health-related quality of life survey (QOL-MV)
  - iii. Confusion Assessment Method for the ICU (CAM-ICU)
  - iv. Tracheostomy-related assessment
    1. Trach size
    2. Mechanical ventilation status
    3. Secretions & tolerance of cuff deflation
    4. Presence of complications
      - i. Bleeding at stoma
      - ii. Subcutaneous air
      - iii. Infection at stomal site
      - iv. Pneumothorax
      - v. Accidental decannulation
  2. Intervention Group completes second SLP evaluation and OWSV trial.
  3. Control Group completes initial SLP evaluation and OWSV trial.
- G. Session 3 following first trach change
1. Both groups receive follow-up SLP re-evaluation and OWSV trials as appropriate per standard of care.

**Setting:** All ICUs at the Johns Hopkins Hospital

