## 6. Drugs/ Substances/ Devices

- a. The rationale for choosing the drug and dose or for choosing the device to be used.

We are not studying the efficacy of the one-way speaking valves. We know that they work. We are studying the timing of when to start using OWSV.

- b. Justification and safety information if FDA approved drugs will be administered for non-FDA approved indications or if doses or routes of administration or participant populations are changed.

N/A

Date: 2/06/18

Principal Investigator: [name]

Application Number: **IRB00080981**

- c. Justification and safety information if non-FDA approved drugs without an IND will be administered.

N/A

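### As scheduled, Hypothesis 3a can compare quality of life only between early valve access and not yet started at 48-60 h; it cannot compare early starters with patients who have already received the valve at 48 h

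*Combined protocol and SAP*

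**What the plan says.** Hypothesis 3a (section 2, Specific Aim 3) states that "The increase in the health-related quality of life scores from pre- to post- assessment will be significantly higher" in the early group "compared to those who receive it the traditional way 48 hours after undergoing a tracheostomy". Section 6a gives the purpose of the trial: "We are studying the timing of when to start using OWSV"; it adds that valve efficacy is not under study.

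Section 4a (Sequence and timing) sets the assessments:

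- "Session 1 within 12-24 hours following percutaneous tracheotomy". Both arms complete the QOL-MV (E.1.iii). The intervention arm then has the SLP evaluation and, if suitable, a valve trial (E.2). Controls have nothing further (E.3).
- "Session 2 within 48-60 hours following percutaneous tracheotomy". Both arms complete the post-assessment, which includes the QOL-MV (F.1.ii). The intervention arm then has its second evaluation and trial (F.2), and finally "Control Group completes initial SLP evaluation and OWSV trial" (F.3).
- Session 3, after the first trach change. Both arms have SLP re-evaluation and valve trials. No QOL-MV is listed.

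Section 7b lists quality of life as a secondary outcome. Section 7c plans 25 patients per arm and names paired t-tests for pre-to-post comparisons of continuous scores.

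**The concern.** The comparator named in H3a is a group that receives the valve at 48 hours. At the only post-baseline QOL-MV, that group has not yet been offered it.

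Two different situations would produce the same Session 2 result. In the first, starting early leaves patients better off than starting at 48 hours, even after the later group has begun. In the second, quality of life improves once a valve is available, and controls gain the same improvement when they start. With no control score after valve use, the data cannot tell these apart.

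What is at stake is interpretation. Taken at its wording, a positive H3a is likely to be reported as an advantage over a 48-hour start. The data would support a narrower statement, about the waiting period only.

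**Working it through.** **The plan's own figure.** Section 7c starts from about 55 eligible patients and allows 10% for non-interest: 55 × (1 − 0.10) = 49.5, rounded to 50, or 25 per arm. This reproduces. It is a feasibility figure; the documents give no significance level, power, effect size or SD.

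**Valve access before each QOL-MV, from section 4a.**

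| Time point | Intervention arm | Control arm |
|---|---|---|
| Session 1 QOL-MV (12-24 h) | none yet | none yet |
| Session 2 QOL-MV (48-60 h) | access since Session 1, if suitable | none |
| After controls have used a valve | no QOL-MV scheduled | no QOL-MV scheduled |

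Lead time in access at the Session 2 score:

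- shortest: 48 − 24 = 24 h
- longest: 60 − 12 = 48 h

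This is time since the valve was first offered, not hours of wear. Section 4d gives the lead as 24-60 h, which the session windows do not produce; the two passages should be reconciled.

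**Controls with a scheduled QOL-MV after valve use:** 0 of 25. This rests on the order of the numbered list in Session 2, since no sentence requires the questionnaire to come first. If the order were reversed, a control would have had one supervised trial in that same session, so the contrast would be nearly the same.

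**What the Session 2 contrast estimates.** Suppose having the valve available raises QOL-MV change by *d* SD, a share *p* of the intervention arm is actually trialed, and early starting has no lasting effect. Then:

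- Session 2 difference between arms = *p* × *d*
- difference after controls have started and caught up = 0

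As an illustration only, take *d* = 0.8, a two-sample t-test on change, 25 per arm and two-sided 5%. None of these except the 25 is in the documents.

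| Share trialed, *p* | Session 2 difference, *p* × *d* (SD) | Chance of significance |
|---|---|---|
| 100% | 0.80 | 79% |
| 70% | 0.56 | 49% |
| 50% | 0.40 | 28% |

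These are ordinary power values for a difference that really exists at Session 2. They are not false-positive rates. They show only that a significant Session 2 result is compatible with no lasting effect of timing.

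**The case against.** The strongest reply is that comparing an early-start policy with a 48-hour policy at a fixed time after tracheotomy is itself a timing question. The abstract motivates the trial by the burden of being without a voice, and section 9a cites the chance of attaining speech sooner. On that rationale, the end of the waiting period is a sensible time to measure. H3a defines its outcome as the change between the two assessments, both are scheduled in both arms, and its comparator can be read as the assigned strategy rather than as prior exposure. This stands: the Session 2 comparison is legitimate and should be kept.

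It also rules out two stronger readings that a reader might infer:

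- *That H3a is untestable.* It is not. A between-arm comparison of change can be made; it answers a narrower question than the wording suggests.
- *That the contrast is valve worn against no valve.* The documents do not support this. The trial at Session 1 is conditional on suitability and may be deferred (sections 4a and 8b), use between sessions depends on recommended supervision and duration, and nothing says the valve is worn during the questionnaire. The contrast is early offer, if suitable, against not yet offered.

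A further objection is that Session 3 is a poor replacement endpoint. Its timing follows the first trach change, with no fixed hour, and section 4f removes patients who are discharged or whose condition prevents continuing the valve trial. This also stands, and is why Session 3 should supplement the Session 2 test rather than replace it.

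What the reply does not supply is any control score after valve use. The ambiguity in H3a's comparator remains until the wording settles it.

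**Conclusion.** The point holds as a limit on what H3a can conclude. As scheduled, H3a can show whether quality of life at 48-60 h is better in patients offered the valve early, if suitable, than in patients not yet offered it. It cannot show whether early starters do better than patients who have received the valve at 48 h, or whether controls catch up.

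The size is structural: 0 of 25 controls scheduled for a score after valve use, against 24-48 h of prior access for suitable early-arm patients. This assumes that Session 2 follows its listed order, and the conclusion barely changes if it does not. It does not depend on the illustrative effect sizes.

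This concerns a secondary outcome in a 50-patient pilot. It is a cheap improvement, not a fault that invalidates the trial.

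**What to change.** 1. Keep the Session 1 to Session 2 comparison as the H3a test, but reword the hypothesis and limit its conclusion. For example: *the change in QOL-MV by 48-60 h after tracheotomy will be greater in patients given early access to the valve than in patients who have not yet started.* State that the test compares change between arms; the paired t-tests in section 7c compare scores within patients and do not test this difference.
2. Add the 12-item QOL-MV at the existing Session 3 in both arms, as a supplementary between-arm comparison of change from Session 1. Report time since tracheotomy at Session 3 and the number removed before Session 3, by arm.

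The rewording costs nothing. The addition costs one more short questionnaire per patient; section 8a already notes that repeated questionnaires can be a burden. Session 3 scores will be incomplete and will come from a selected group, so they should be presented as supportive. No clinical procedure changes. If the Session 3 score is not added, the rewording should still be made.

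### Hypothesis 3b makes a non-significant complication difference the predicted safety result, with no between-arm analysis, margin or confidence interval at 25 per arm

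*Combined protocol and SAP*

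**What the plan says.** The Abstract states the purpose: "we propose a prospective randomized clinical trial - pilot study to investigate the safety of early use of OWSV". Under Specific Aim 3, Hypothesis 3b predicts: "There will be no significant changes in the rate of complications between patients receiving early versus standard use of the OWSV".

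Section 7a makes speech intelligibility the primary outcome. Section 7b lists complications among the secondary outcomes, gives no time window, and points to a codebook that is not part of the document. Section 7c describes its chi-square and Fisher tests only as comparisons of pre- with post-assessment. It states no alpha, expected complication rate, margin or interval. The 25 per arm come from patient availability. Section 7d halts the study for major complications arising from the early valve trial.

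Section 4a sets the timing:
- **Session 1:** "Session 1 within 12-24 hours following percutaneous tracheotomy". Both groups have a five-item complication checklist in the pre-assessment (E.1). The intervention group then has its evaluation, and "If appropriate, OWSV will be trialed and assessed for the following" introduces the valve trial (E.2). One item recorded in that trial is "Presence of air trapping".
- **Session 2:** "Session 2 within 48-60 hours following percutaneous tracheotomy". Item F.1 is "Both groups complete post-assessment", which contains the same checklist. Item F.3 is "Control Group completes initial SLP evaluation and OWSV trial".
- **Session 3:** after the first tracheostomy tube change. It lists re-evaluation and valve trials, but no complication checklist.

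Section 4f removes patients whose clinical condition prevents the valve trial from continuing, or who are discharged.

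**The concern.** A non-significant test in a small trial is weak evidence of similar risk. If non-significance is the predicted result, the less the trial can detect, the more likely the prediction is to be met. H3b is in that position: it carries the stated purpose of the pilot, yet no planned statistic shows how large an excess of complications would remain compatible with the data. H3b compares arms, while the only categorical tests described compare time points, so the analysis that would decide it is not written down. Two tests are named without a rule for choosing between them, and at this size they can disagree.

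Two features of data collection add to this. As listed, the last checklist comes before the control arm's first valve use, so it does not cover complications after standard-timed use begins. And nothing says that complications in patients removed under 4f still count, although the change in condition that triggers removal may itself be a complication.

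**Working it through.** **Inputs from the plan.** N = 50, 25 per arm (7c); Session 1 at 12–24 h and Session 2 at 48–60 h (4a). The plan's own sample size is a feasibility count: 55 × (1 − 0.10) = 49.5, about 50. It reproduces. No power figure is given, so there is none to check.

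**Assumptions.** Two-sided 0.05 test between arms, and illustrative complication rates; the document gives neither.

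**1. Chance that H3b is met when early use is worse.** For each pair of rates, all 26 × 26 possible tables were enumerated. The binomial probabilities, Bin(25, p_control) × Bin(25, p_early), were summed over tables that do not reach p ≤ 0.05.

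| True rates, standard vs early | Non-significant, Fisher | Non-significant, uncorrected chi-square |
|---|---|---|
| 5% vs 15% | 93% | 79% |
| 10% vs 20% | 91% | 83% |
| 5% vs 20% | 80% | 62% |
| 10% vs 30% | 70% | 55% |

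If removals left 20 per arm (assumed), the Fisher column would read 93%, 93%, 83% and 76%.

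**2. Single results.** With a events in the early arm and b in the control arm, chi-square = 50 × [a(25 − b) − b(25 − a)]² / [25 × 25 × (a + b) × (50 − a − b)]. For 5 vs 0 this is 50 × 125² / (625 × 5 × 45) = 5.56, p = 0.018. The Newcombe interval combines the two Wilson intervals: lower limit d − √[(p1 − l1)² + (u2 − p2)²], upper limit d + √[(u1 − p1)² + (p2 − l2)²].

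| Early vs control | Difference | Fisher p | Chi-square p | Newcombe 95% CI, points |
|---|---|---|---|---|
| 5/25 vs 0/25 | 20 | 0.0502 | 0.018 | +2.6 to +39.1 |
| 6/25 vs 1/25 | 20 | 0.098 | 0.042 | +0.1 to +39.7 |
| 8/25 vs 2/25 | 24 | 0.074 | 0.034 | +1.5 to +44.4 |
| 2/25 vs 2/25 | 0 | 1.0 | 1.0 | −17.9 to +17.9 |
| 0/25 vs 0/25 | 0 | 1.0 | not defined | −13.3 to +13.3 |

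In the first three rows H3b is met by Fisher and contradicted by chi-square; the interval agrees with chi-square. For 0 vs 0, each Wilson upper limit is 13.3%, which gives ±13.3 points.

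**3. What the listed checklists cover.** For an early-arm patient actually given the valve at Session 1, the time to the Session 2 checklist is at least 48 − 24 = 24 h and at most 60 − 12 = 48 h. In the listed order, a control patient has no valve time before that checklist, or at most same-session follow-up if the order is not kept. The contrast is therefore early valve against waiting, up to 48–60 h after tracheotomy in both arms.

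**The case against.** The best defence is context. This is a labelled pilot, complications are secondary, and N was never presented as powered. That stands, and it is why the remedy is an interval and not a larger trial.

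A second objection is that Fisher alone exaggerates the problem. That also stands in part. Chi-square, which 7c names too, flags all three of the lopsided tables above, as do their Newcombe intervals, and it lowers the chance of non-significance appreciably, to near an even chance for 10% vs 30%. Convention would also favour Fisher for 5 vs 0, where the smallest expected count is 5 × 25/50 = 2.5, so the choice of test is not wholly open there. For 8 vs 2 the count is 10 × 25/50 = 5.0 and chi-square would usually be accepted. After these concessions a 10-point excess is still missed in at least 79% of trials.

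Third, 7d would stop the study for major complications attributed to early use, so large excesses would mostly be minor or unattributed events. That limits the scenarios, but it supplies no between-arm estimate.

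A reader might infer more than the document supports:
- **That the sponsor will declare safety from p > 0.05.** The protocol does not say so; the wording of H3b only invites it.
- **That complications after control valve use go unrecorded.** This cannot be established. The order within Session 2 is read from the numbering, 7b lists time to events and mortality, participation is estimated at 4 weeks, 8b has valve trials discontinued and referred to the medical team if complications occur, and the codebook is not supplied.
- **That the Session 2 contrast is invalid.** It is a legitimate randomised comparison over the period when only one arm has been offered the valve, which is where added risk from early use would mainly fall. It needs an accurate label.

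**Conclusion.** The point holds as a should-fix. H3b, as worded, is likely to be met under true excesses of 10 points with either named test, and more often than not under excesses of 15 to 20 points. No planned figure would show what excess remains possible. These sizes rest on assumed complication rates, a two-sided 0.05 level and 25 analysed patients per arm. The absence of a between-arm analysis, margin or interval rests on the text alone and is firm.

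The checklist gap is secondary and less certain, because it depends on the listed order and on what the codebook contains. The 4f point is likewise a silence in the plan: it does not show that events will be discarded.

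**What to change.** **1. Restate H3b as estimation.** Suggested wording: 'We will estimate the as-randomised difference, early minus standard, in the proportion of patients with at least one new complication between Session 1 and Session 2, with a 95% Newcombe confidence interval. The interval is the H3b result. We will state the largest excess not ruled out and will not infer equal safety from p > 0.05.' Naming the interval matters because it and Fisher can disagree, as for 5/25 vs 0/25.

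**2. Label that comparison** 'early valve versus waiting'. It is preferred for H3b because both arms share the same window, ending 48–60 h after tracheotomy.

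**3. Count complications in patients removed under 4f** in their randomised arm, as far as they were observed.

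**4. Supportive: extend collection.** Unless the codebook already does so, repeat the five-item checklist with onset time at Session 3 in both arms. Report complications through Session 3 with follow-up time by arm, for example as events per patient-day. This should not replace the Session 2 comparison. Follow-up then ends at a variable tube change or at discharge, and may differ by arm, since H3c predicts shorter ICU stays with early use.

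**Cost.** Items 1 and 2 are wording. Items 3 and 4 add a few checklist entries at an existing visit, onset and follow-up times, and complication data on removed patients. The real downside is a visibly less certain safety statement: even with equal true rates of 5%, 10% or 20%, the median upper limit would be about +16, +18 or +22 points.

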**Study Protocol**

Date: 2/06/18

Principal Investigator: [name]

Application Number: **IRB00080981**

- b. Study duration and number of study visits required of research participants.

The study duration is estimated to be 4 weeks per patient with a total of 3 visits by the study team.

- c. Blinding, including justification for blinding or not blinding the trial, if applicable.

Patients will not be blinded to intervention or control group.

- d. Justification of why participants will not receive routine care or will have current therapy stopped.

If patient is not willing to participate in the study, their routine care will not be altered. Participants in the control group will receive routine care, and participants in the intervention group will initiate the same intervention as routine care with timing to be 24-60 hours earlier than the current routine care.

- e. Justification for inclusion of a placebo or non-treatment group.

N/A

- f. Definition of treatment failure or participant removal criteria.

If there is a change in clinical condition that prevents study team from continuing with OWSV trial or if the patient is discharged from the hospital, the patient will be removed from the study.

- g. Description of what happens to participants receiving therapy when study ends or if a participant's participation in the study ends prematurely.

If participants receiving the OWSV complete the study (after Session 3), they will continue to use the OWSV per our current standard of care. If the participant's participation using the OWSV ends prematurely due to change in clinical condition, then they will be dropped from the study. But if their condition improves and warrants reuse of the OWSV, they will be offered the OWSV per our standards of care but will not be re-enrolled in the study.

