## 7. Study Statistics

- a. Primary outcome variable.

Speech intelligibility

- b. Secondary outcome variables.

- Patient characteristics
- Quality of Life
- Complications
- Time to events
- Length of stay
- Mortality

\*See codebook for list of additional variables

- c. Statistical plan including sample size justification and interim data analysis.

Mean, standard deviation, median and inter-quartile range will be calculated for continuous variables. Paired t-tests will be used to compare pre and post assessment scores for continuous variables. Frequencies and percentages will be calculated for categorical variables. Chi square and Fisher Exact tests will be used to compare pre and post assessment scores of categorical variables. Sample size is estimated based on 30% of tracheostomy patients who might be awake and interactive at the Johns Hopkins Hospital in 2016, as per the tracheostomy database. According to the 2014 data, we found that about 55 patients were awake and interactive while having a percutaneous tracheostomy tube at the hospital. Considering a 10% of the patients who may not be interested in the study, we will plan for a sample size of 50 with 25 in the intervention group and 25 in the control group.

- d. Early stopping rules.

If patients have changes in clinical condition that prevents cuff deflation, they will be dropped from the study. The study will be halted if any major complications occur from early trial of OWSV.

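### Hypothesis 3b agrees with a non-significant complication comparison, but 25 per arm with no margin cannot support a no-harm reading at low-to-moderate complication risks

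*Combined protocol and SAP*

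**What the plan says.** The Abstract gives the aim of the pilot as to "investigate the safety of early use of OWSV in patients undergoing a percutaneous tracheostomy". Under Specific Aim 3, Hypothesis 3b reads: "There will be no significant changes in the rate of complications between patients receiving early versus standard use of the OWSV". The other comparative hypotheses (2a, 3a and 3c) each predict a significant difference in favour of early use.

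Section 7 makes speech intelligibility the primary outcome and lists complications as secondary. On size, 7c states "we will plan for a sample size of 50 with 25 in the intervention group and 25 in the control group", based on a 2014 count in which "we found that about 55 patients were awake and interactive while having a percutaneous tracheostomy tube at the hospital", less 10% for refusals. On tests, it states "Chi square and Fisher Exact tests will be used to compare pre and post assessment scores of categorical variables". It names no between-arm test for complications and gives no alpha, power, margin, expected complication rate or confidence interval.

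Section 4a lists "Presence of complications" (five types) in the Session 1 pre-assessment, before any valve trial, and again in the Session 2 post-assessment. Section 4f says that "if the patient is discharged from the hospital, the patient will be removed from the study", and also removes patients whose clinical condition prevents the valve trial from continuing. Section 7d adds: "If patients have changes in clinical condition that prevents cuff deflation, they will be dropped from the study". Separately, 7d halts the study if an early valve trial causes a major complication.

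**The concern.** For 2a, 3a and 3c a small sample works against the hypothesis. For 3b it works in favour: the less information the trial yields, the more likely a result that agrees with the prediction. With no margin or interval, nothing in the plan separates a result showing similar risks from one that is merely uninformative.

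The question behind the trial is whether the customary 48-hour wait can be shortened safely. A statement that complications did not differ significantly would be natural support for shortening it, even if the data still allowed a large excess risk.

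Two details also affect what would be compared. The documents supplied do not say whether complications already present at Session 1 count. Nor do they say where patients removed under 4f or dropped under 7d belong, although some of those removals may be related to harm.

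**Working it through.** **The plan's own figure.** 55 × (1 − 0.10) = 49.5, which rounds to the stated 50, or 25 per arm. It reproduces, and it is a count of available patients rather than a calculation for any outcome.

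**Inputs.** From the documents: 25 per arm, Fisher and chi-square as the named categorical tests, no margin. Assumed, because the documents give none: control risk p from 5% to 40%, true early-arm risk 2p, two-sided 0.05.

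**Method.** With X the control count and Y the early count,

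P(significant, early worse) = Σ Bin(x; 25, p) × Bin(y; 25, 2p), summed over all (x, y) with y > x and test p-value < 0.05.

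**Chance that a true doubling is significant**

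| Control v early risk | Fisher, 25 per arm | Uncorrected chi-square, 25 per arm | Fisher, 20 per arm |
|---|---|---|---|
| 5% v 10% | 1.3% | 7.8% | 1.6% |
| 10% v 20% | 8.5% | 17% | 7.2% |
| 15% v 30% | 15% | 26% | 12% |
| 20% v 40% | 23% | 35% | 19% |
| 25% v 50% | 36% | 48% | 27% |
| 30% v 60% | 51% | 62% | 35% |
| 40% v 80% | 79% | 87% | 65% |

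At 25 per arm the chance passes one half at a control risk of about 30% with Fisher (49.1% at 29.5%, 50.6% at 30%) and about 26% with uncorrected chi-square. The last column assumes that removals leave 20 per arm; the Fisher break-even then moves to about 36%.

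**Observed splits (early v control) that Fisher leaves non-significant at 25 per arm.** 5 v 0: p = 2 × C(25,5)/C(50,5) = 0.0502. 6 v 1: p = 0.098. 8 v 2: p = 0.074. The nearest significant splits are 6 v 0 (0.022), 7 v 1 (0.049) and 9 v 2 (0.037). These cut-offs belong to Fisher; uncorrected chi-square would call 5 v 0, 6 v 1 and 8 v 2 significant (0.018, 0.042 and 0.034).

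**What intervals would show**
- 0/25 in the early arm: exact upper limit 1 − 0.025^(1/25) = 13.7%.
- 2/25 v 2/25: difference 0, Newcombe 95% interval −17.9 to +17.9 points.
- 5/25 v 2/25: Fisher p = 0.42; difference 20% − 8% = +12 points, Newcombe 95% interval −8.3 to +32.0 points. This result agrees with 3b, yet it does not exclude an excess of about 32 points.

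**Which exposure is compared.** In the order listed in 4a, the Session 2 complication check (F.1) comes before the control group's first valve trial (F.3). The Session 1 to Session 2 comparison is therefore early valve use against no valve yet. Air trapping, which Section 8a names as a valve risk, is not among the five listed complications; it is assessed during the valve trial.

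**The case against.** The strongest reply is that 3b is an expectation, not a decision rule. A reader might infer that the investigators plan to declare early use safe if the test is non-significant. The documents do not support that: nothing in Section 7 says how such a result will be reported, and 7c already plans frequencies and percentages for categorical variables, from which intervals could be derived if they are given by arm. This stands, and it limits the point to wording and analysis. It does not remove it, because 3b is still the only between-arm criterion stated and no interval is planned.

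A reader might also infer that patients are unprotected or that complications have no other criterion. That is not so. Section 7d halts the study for major complications from early trials, and 8b provides for assessment by the speech-language pathologist, deferral, and stopping the trial with referral. These protect participants but do not say how the arms are to be compared.

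Nor would the trial miss every harm. Under Fisher at 25 per arm, 5% v 30% is significant 55% of the time and 5% v 35% 70% of the time. The doubling is an illustration, not a clinical threshold from the plan.

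Finally, 7b refers to a codebook that is not among the documents. It may define which complications count, so the remark about complications already present applies only to what was supplied.

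**Conclusion.** The point holds and is minor. With 25 per arm and no margin, a true doubling of complication risk would more often than not be non-significant at control risks below about 26% to 30%, depending on the test. At 5% to 20% control risk, Fisher detects it 1.3% to 23% of the time. The control risks, the doubling and the two-sided 0.05 level are assumptions. A non-significant result would agree with 3b but would not be evidence of no harm. Severity is limited because this is a pilot, complications are secondary and the halting rule stands apart from the test. The stated safety purpose is the reason to correct it all the same.

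**What to change.** Recast Hypothesis 3b and Section 7c as estimation, for example:

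- Report, by assigned arm, the five listed complications newly recorded after the Session 1 pre-assessment and up to the Session 2 check. Give the early-arm risk with an exact 95% confidence interval and the between-arm difference with a Newcombe 95% interval.
- State that this compares early valve use with no valve yet, because the Session 2 check is listed before the control arm's first valve trial.
- Report air trapping during valve trials separately, by arm.
- Count removed patients with the complications recorded up to removal, and give the number removed by arm.
- State that a non-significant test is not taken as evidence of safety.

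The cost is a few sentences, two intervals and two tallies by arm (air trapping and removals), from data the plan already records, with no added patients or visits. Events after removal would still be missed. The no-difference claim is given up and the intervals will be wide, which is a fair picture of what 25 per arm can show.
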